11.5 Protocol Violations and Deviations

A deviation from the protocol is an unintended and/or unanticipated departure from the procedures and/or processes that were approved by the Sponsor and the IRB, and that were agreed to by the Principal Investigator. Deviations usually have an impact on individual patients or a small group of patients and do not involve inclusion/exclusion or primary endpoint criteria. A protocol violation occurs when (1) there is non-adherence to the protocol that results in significant additional risk to the patient, (2) the patient or Principal Investigator has failed to adhere to significant protocol requirements (e.g., inclusion/exclusion criteria), or (3) there is non-adherence to FDA regulations and/or ICH E6(R1) guidelines.

For this protocol, violations will be defined as exceptions to the inclusion or exclusion criteria, situations where a patient is required to withdraw but the investigator believes the patient should remain in the study, and the use of an excluded concomitant medication. All other departures from the protocol (e.g., missed visit windows, laboratory samples not collected on the required day) will be documented as protocol deviations. The Principal Investigator or designee must document and explain any protocol deviation or violation in the patient's source documentation. The investigator should notify the IRB of all protocol violations and deviations per local institutional policy. Protocol deviations and violations will be documented by the responsible clinical site monitor during monitoring visits, and those observations will be reviewed with the investigator.

The Principal Investigator may implement a change from the protocol without prior Sponsor and IRB approval only to eliminate an immediate hazard to a patient. The implemented change should be submitted to the IRB for review as soon as possible.

If the investigator believes that an exception to the protocol is justified for an individual patient, the investigator may present the facts and rationale to the medical monitor and request a one-time

exception. This request will be submitted in writing on a protocol inquiry form, which will be faxed to the medical monitor for review and disposition. The medical monitor will then fax the decision to the investigator regarding approval or denial of the request. This written documentation must be filed in the investigator's study file.

This process will apply if the investigator believes that a patient should receive an excluded concomitant medication and remain in the study, or if the investigator believes that a patient should remain in the study when the protocol dictates that the patient should be discontinued. The implemented change should be submitted to the IRB for review as soon as possible. However, it is the policy of the Sponsor that there will be no exceptions granted concerning the inclusion and exclusion criteria.

11.6 Study Reporting Requirements

By participating in this study, the Principal Investigator agrees to submit reports of AEs according to the timeline and method outlined in the protocol. In addition, the Principal Investigator agrees to submit periodic reports to his/her IRB as appropriate.

11.7 Financial Disclosure and Obligations

Principal Investigators and subinvestigators are required to provide financial disclosure information to allow the Sponsor or designee to submit the complete and accurate certification or disclosure statements required under Title 21 CFR 54. In addition, the Principal Investigator and subinvestigators must provide the Sponsor or designee with a commitment to update this information promptly, if any relevant changes occur during the course of the investigation and for 1 year following the completion of the study.

The Sponsor or designee is not financially responsible for further testing/treatment of any medical condition that may be detected during the Screening process. In addition, in the absence of specific arrangements, the Sponsor or designee is not financially responsible for treatment of the patient's disease.

11.8 Investigator Documentation

Before beginning the study, the Principal Investigator will be asked to comply with ICH E6(R1) 8.2, Title 21 CFR, and other applicable regulatory requirements by providing the essential documents to the Sponsor or designee, which include but are not limited to the following:

- An original Investigator-signed investigator agreement page of the protocol
- Documentation of IRB approval of the protocol and informed consent
- The IRB-approved informed consent, samples of site advertisements for recruitment for this study, and any other written information regarding this study that is to be provided to the patient or legal guardians.
- A Form FDA 1572, fully executed, and all updates on a new fully executed Form FDA 1572.
- Curricula vitae for the Principal Investigator and each subinvestigator listed on Form FDA 1572. A copy of the current license must be provided. The curricula vitae must be signed and dated by the Principal Investigators and subinvestigators within 1 year before study start-up to indicate that the documents are accurate and current.
- Completed financial disclosure forms to allow the Sponsor or designee to submit complete and accurate certification or disclosure statements required under Title 21 CFR 54. In addition, the investigators must provide to the Sponsor or designee with a commitment to update this information promptly if any relevant changes occur during the course of the investigation and for 1 year following the completion of the study ([Section 11.7](#)).
- Laboratory certifications and normal ranges for any local laboratories used by the site, in accordance with Title 42 CFR 493.

11.9 Study Conduct

The Principal Investigator agrees that the study will be conducted according to the principles of ICH E6(R1), the principles of the World Medical Association Declaration of Helsinki, and regulatory requirements of the US FDA and TFDA. The Principal Investigator will conduct all aspects of this study in accordance with all national, state, and local laws or regulations.

#### 1. Introduction

This document outlines the planned statistical analyses for data collected within the scope of the TaiMed ibalizumab protocol TMB-311, entitled "A Phase 3, Multicenter, Expanded Access Study of Ibalizumab Plus an Optimized Background Regimen (OBR) in Treatment-Experienced Patients Infected With Multi-Drug Resistant (MDR) HIV-1". This statistical analysis plan (SAP) applies to the most recent version of the study protocol (dated 11 December 2017) and will be updated as necessary if future protocol amendments warrant an update to the manner of analysis. This document was prepared in accordance with the International Conference on Harmonisation (ICH) Guideline E3: Structure and Content of Clinical Study Reports [1].

## 2. Study Overview

## 2.1. Study Design

This Phase 3 multicenter study will evaluate safety and tolerability of ibalizumab in HIV positive patients with MDR HIV infection. Eligible patients will include those currently receiving ibalizumab under a TaiMed-sponsored or Investigator-INDprotocol, and treatment-experienced patients with no history of ibalizumab treatment who are on a failing regimen, or who have failed and are off treatment. Patients will be enrolled in one of two Cohorts. Cohort 1 consists of patients currently receiving ibalizumab via other TaiMed-sponsored or Investigator-IND (compassionate use) protocols. These patients will continue their current dosage of ibalizumab (800 mg every 2 weeks or 2000 mg every 4 weeks). Cohort 2 consists of patients initiating ibalizumab. These patients will receive a 2000 mg loading dose at Baseline/Day 0 followed by 800 mg maintenance doses every 2 weeks.

For Cohort 1, screening procedures and Day 0 procedures are scheduled for the same day. Patients who qualify for entry into Cohort 1 of this study who are currently receiving 800 mg ibalizumab every 2 weeks will have physical and laboratory measures performed and receive the first on-study dose of ibalizumab at Screening/Day 0. These patients will return to the clinic on Day 14 and every 2 weeks thereafter through the remainder of participation in the study (up to 144 weeks) for study drug administration (800 mg) and effectiveness and safety evaluations. Patients who are discontinued or who withdraw from the study prematurely will be asked to return for an Early Withdrawal visit to have all assessments detailed in the Schedule of Events for that visit performed.

Patients who qualify for entry into Cohort 1 of this study who are currently receiving 2000 mg ibalizumab every 4 weeks will have physical and laboratory measures performed, and receive the first on-study dose of ibalizumab at Screening/Day 0. These patients will return to the clinic at Week 4 and every 4 weeks thereafter through the remainder of participation in the study (up to 144 weeks) for study drug administration (2000 mg) and effectiveness and safety evaluations. Patients who are discontinued or who withdraw from the study prematurely will be asked to return for

an Early Withdrawal visit to have all assessments detailed in the Schedule of Events for that visit performed.

For Cohort 2, patients will complete all screening procedures during the six weeks before Baseline/Day 0. Successful screening results will allow the patients to proceed to the Baseline/ Day 0 Visit, where they will initiate the selected OBR in addition to undergoing physical and laboratory measures. At this visit patients will also receive the loading dose of the study medication (2000 mg). Patients will return to the clinic on Day 7 for effectiveness and safety evaluations, and on Day 14 and every two weeks thereafter through the remainder of participation in the study (up to 144 weeks) for study drug administration (800 mg) and effectiveness and safety evaluations. Patients who are discontinued or who withdraw from the study prematurely will be asked to return for an Early Withdrawal visit to have all assessments detailed in the Schedule of Events for that visit performed.

All patients who complete Week 144 or end of study (EOS) visit will return for a follow-up visit at Week 150. Patients may be discontinued from the study at the patient's request or if the patient becomes pregnant, at investigator request, for a protocol violation, for treatment-related serious or intolerable adverse events (AEs), for toxicity (defined as two consecutive laboratory results, at least 14 days apart, with a CD4+ T-cell count below 200 cells/mm3 that also represents a 50% reduction from the Baseline CD4+ T-cell count), or for virologic failure. Virologic failure is defined as two consecutive measurements beginning at Week 24 or later if less than a 0.5 log10 decline from the Baseline viral load.

## 2.2. Study Objectives

## 2.2.1. Primary

The primary objectives of this study are to:

#### Cohort 1

- Continue to provide ibalizumab to patients currently receiving ibalizumab treatment under Investigator-sponsored INDs or TaiMed-sponsored protocols
- Demonstrate the safety and tolerability of ibalizumab in HIV positive patients with MDR HIV infection

#### Cohort 2

- Provide access to ibalizumab for qualifying MDR HIV-1 infected patients with limited treatment options
- Demonstrate the safety, efficacy, and tolerability of ibalizumab in HIV positive patients with MDR HIV infection

## 2.2.2. Secondary

The secondary objectives of this study are to:

- Demonstrate the antiviral activity of ibalizumab in HIV positive patients with MDR HIV infection
- Characterize HIV-1 sensitivity/susceptibility changes associated with protocol-defined virologic failure after ibalizumab administration in combination with OBR
- Determine the presence and significance of anti-ibalizumab antibodies associated with protocol-defined virologic failure after ibalizumab administration, if any (immunogenicity of ibalizumab)

## 2.3. Study Drug Dosage and Administration

The investigational product, ibalizumab, is a humanized IgG4 monoclonal antibody (MAb) administered via intravenous (IV) infusion. Patients will be enrolled in one of two Cohorts (Cohort 1 and Cohort 2). Cohort 1 patients will continue their current dosage of ibalizumab (800 mg every 2 weeks or 2000 mg every 4 weeks). Cohort 2 patients will receive a 2000 mg loading dose at Baseline/Day 0 followed by 800 mg maintenance doses every 2 weeks.

Patients receiving ibalizumab under Investigator-IND protocols, who will enroll into Cohort 1 of this study, are currently being supplied with ibalizumab vials containing a 1.2 mL injection volume and 180 mg ibalizumab per vial. For this study, these patients will continue receiving ibalizumab in this vial configuration until that supply of drug product is exhausted, at which time they will be switched to the drug product with a 1.33 mL injection volume and 200 mg ibalizumab per vial.

Patients receiving ibalizumab in study TMB-301, who will enroll into Cohort 1 of this study, and patients initiating ibalizumab in Cohort 2 will receive only vials with a 1.33 mL injection volume and 200 mg ibalizumab per vial. During this study, it will be very important to ensure that all drug supplies are clearly labeled and segregated by vial configuration to prevent confusion.

In addition to the study drug, all patients will receive an OBR, which is a standard—of-care regimen selected by the investigator based upon treatment history and the results of recent viral resistance testing. For patients enrolling into Cohort 2, previous resistance testing done within 6 months prior to Screening must demonstrate that the patient's viral isolate is sensitive/susceptible to a minimum of one of the agents selected for the OBR. The patient must be willing and able to take at least one of the agents to which their virus is sensitive/susceptible as part of the OBR.

#### 2.4. Procedures

#### 2.4.1. Patient Identification

Once consent is obtained and study eligibility has been determined, a patient will be enrolled into the study and will be assigned a Participant Identification (PID) number. The 5-digit PID number will consist of a 2-digit site number and a 3-digit sequential patient number. If a patient in Cohort 2 is a screen failure, the PID number will not be reassigned.

## 2.4.2. Randomization

This will be an open-label, non-randomized study.

## 2.4.3. Blinding/Unblinding

There will be no blinding/unblinding considerations for this open-label, non-randomized study.

## 2.4.4. Replacement

Patients who withdraw or otherwise discontinue the study prematurely will not be replaced.

#### 3. Statistical Analysis Considerations

## 3.1. Sample Size

Anticipated enrollment is approximately 100 patients from approximately 50 sites in North America; however, the numbers of participating patients and sites will not be limited and may exceed 100 patients.

## 3.2. Analysis Populations

## 3.2.1. Intent-to-Treat (ITT) Population

The ITT population is defined as all patients enrolled into the TMB-311 study. The ITT Analysis Population will be used for the patient disposition, demographic and physical characteristics, and efficacy analyses.

If there are ITT patients who do not receive at least one complete dose of study drug, then a modified ITT (mITT) Analysis Population will be used for a supportive effectiveness analysis.

## 3.2.2. Safety (SAF) Population

All patients who receive at least one partial dose of study drug will be included in the SAF Population. Patients will be analyzed according to the treatment they actually received. The SAF Population will be used for the safety analyses.

## 3.3. Data Handling

#### 3.3.1. Measurement Times

The nominal visit time point entered on the electronic case report forms (eCRFs) will be used. Patients are asked to adhere to the following visit schedule (with windows in parentheses):

- For Cohort 1 patients, Screening and Day 0 (first on-study administration of ibalizumab) are scheduled for the same day.
- For Cohort 2 patients, the Screening will occur 1 to 6 weeks prior to Day 0.
- For Cohort 2, Day 7 (+/- 1 day) serves as the time point at which the antiviral activity of ibalizumab will be assessed to address the primary effectiveness objective.
- For all Cohorts, Day 14 (+/- 1 day) and Week 4 (+/- 2 days) through Week 144/EOS Visit (+/- 2 days) from the Day 0 date (Visit Week will depend on the dosing schedule per Cohort 1 or 2; please refer to the Schedule of Visits Tables 3.1-3.6 in the study protocol).

## 3.3.2. Clinical Laboratory Data Handling Conventions

If a patient has multiple results in the clinical laboratory data for the Screening visit, only the last result prior to the first dose of study drug will be included in the analysis. If a patient has multiple results (retests) for subsequent visits, the retest results will only be included in the analysis if the patient does not have a value recorded for the original assessment at the given visit.

#### 3.3.3. Baseline Values

For patients in Cohort 1 who were enrolled in the TMB-202 or TMB-301 studies, Baseline values for TMB-311 are defined as the values recorded for the Baseline visit in the previous study. For patients in Cohort 1 who were not enrolled in the TMB-202 or TMB-301 studies as well as for patients in Cohort 2, Baseline is defined as the last assessment prior to their first dose of study drug on the TMB-311 Day 0 visit.

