3.1 Overall Design

This Phase 3, multicenter, expanded access study will evaluate the safety and tolerability of ibalizumab in treatment-experienced patients infected with MDR HIV-1. Eligible patients will include (1) those currently receiving ibalizumab under a TaiMed-sponsored or Investigator-sponsored IND protocol and (2) treatment-experienced patients with no history of ibalizumab treatment who are on a failing regimen, or who have failed and are off treatment.

Patients will be enrolled in one of two Cohorts (Cohort 1 and Cohort 2):

Cohort 1 (continuing treatment)

- Patients will continue on an ibalizumab containing regimen at their current dosage in combination with a current OBR.

Cohort 2 (initiating ibalizumab)

- On Day 0/Baseline, patients will receive one 2,000 mg dose (loading dose) of ibalizumab. The OBR will be initiated on Day 0/Baseline and must include at least one agent to which the patient's virus is susceptible.
- Beginning at Day 14, an 800 mg of ibalizumab will be administered every 2 weeks through the remainder of the study.

Virologic failure is defined as two consecutive measurements at Week 24 or later if less than a 0.5 log₁₀ decline from the Baseline viral load (see Section 9.4 for the definition of Baseline).

Patients will be discontinued from the study at the patient's request or if the patient becomes pregnant, at investigator request, for protocol violation, for virologic failure, for treatment-related serious or intolerable AE(s) (Division of AIDS [DAIDS] criteria, see Appendix B), or for toxicity (defined as two consecutive laboratory results, at least 14 days apart, with a CD4⁺ cell count below 200 cells/mm³ that also represents a 50% reduction from the Baseline CD4⁺ cell count).

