5.1 Inclusion Criteria

Patients may be enrolled in Cohort 1 if they meet both of the following criteria:

1. Are currently receiving ibalizumab via other TaiMed-sponsored or Investigator-sponsored IND protocol
2. Are capable of understanding and have voluntarily signed the informed consent document

Patients may be enrolled in Cohort 2 if they meet all of the following criteria:

1. Are 18 years of age or older
2. Are capable of understanding and have voluntarily signed the informed consent document
3. Have documented HIV-1 infection by official, signed, written history (e.g., laboratory report); otherwise, an HIV-antibody test will be performed
4. Are able and willing to comply with all protocol requirements and procedures
5. Have a viral load >1,000 copies/mL and documented resistance to at least one antiretroviral medication from each of three classes of antiretroviral medications as measured by previous resistance testing (resistance testing is not provided by the study for qualification purposes)
6. Have a history of at least 6 months on antiretroviral treatment
7. Are receiving a failing antiretroviral regimen OR have failed and are off therapy
8. Have viral sensitivity/susceptibility to at least one antiretroviral agent other than ibalizumab, as determined by previous resistance test performed within 6 months prior to Screening and be willing and able to be treated with at least one agent to which the

patient's viral isolate is fully sensitive/susceptible according to the Screening resistance tests as a component of the OBR

9. If sexually active, are willing to use an effective method of contraception during the study and for 30 days after the last administration of the study drug

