9.4 Definition of Baseline

For patients in Cohort 1 who were enrolled in the TMB-202 or TMB-301 studies, Baseline values for TMB-311 are defined as the values recorded for the Baseline visit in the previous study. For patients in Cohort 1 who were not enrolled in the TMB-202 or TMB-301 studies, Baseline values for TMB-311 are defined as the last values recorded prior to receiving the first dose of ibalizumab. For patients in Cohort 2, Baseline is defined as the Day 0 visit of TMB-311 (this study).

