## 4.5.2.3 Virologic Outcome

## Snapshot Approach

Virologic outcome will be assigned for each patient at each key visit after Week 12 [Weeks 24, 48, 72, 96, 120, and 144/EOS], per the snapshot approach, using the following standard categories:

- 1=Virologic success (≥0.5 log10 decline from Baseline in viral load)
- 2a=(<0.5 log10 copies/mL drop from Baseline in viral load)
- 2b=Discontinued efficacy portion of study because of virologic failure (may still continue safety)
- 2c=Discontinued because of other reasons and the drop from baseline in viral load at the time of discontinuation was <0.5 log10 copies/mL
- 2d=OBR changed
- 3a=Discontinued because of AE or death
- 3b=Discontinued because of other reasons and the drop from baseline in viral load at the time of discontinuation was >=0.5 log10 copies/mL
- 3c=Missing data during the window but on study

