**CONFIDENTIAL** 

# **Notes Applicable to All Listings**

#### General Programming Notes:

- 1. There are a few listings that might fit as they are or might have to be split once we see the output with actual data.
- 2. All listings should start with and be sorted by Patient ID (concatenation of site number and patient number) and then visit date as appropriate.
- 3. If columns with specific text should be widened due to the amount of text, it is up to the programmer's discretion. However, please keep to the industry standard margin of 1 inch on bottom and sides and 1.25 inches on the top. Font is Courier New 8 point.
- 4. For all dates used, character format dates to capture partial dates. Use dashes where a month or day is missing. If entire date is missing just leave blank. i.e., JAN2011 or 01-2011.
- 5. If a programming note appears on the mock listing indicating that the footnote should appear only on the first page, this means the first page of output contains all footnotes and ONLY footnotes. All subsequent pages contain data with one footnote that says "Refer to page 1 for footnotes".
- 6. Some of the mock tables display numbers rather than x's. The numbers are meaningless and are for example only. Where visit names are displayed in tables, these are examples as well. Correct visit names for the TMB-311 study should be displayed in the actual output.
- 7. Each listing should include all applicable data, even if only a subset of the full set of treatment groups is displayed in the mocks. And unlike the tables and graphs, the listings should also include the 2 PI-IND rollover patients.
- 8. Sort each listing by Treatment and then Patient ID where applicable.

Listing 16.2.1.1

Patient Disposition

Treatment	Patient ID Sc	reened	ITT Population [1]	SAF Population [2]	
C1:301/800mg	311-XX-XXX	YES	YES	YES	
C1:202/800mg	311-XX-XXX	YES	YES	YES	
C1:202/2000mg	311-XX-XXX	YES	YES	YES	
C2:800mg	311-XX-XXX	YES	YE:	S YES	

Intent-to-Treat (ITT) Population consists of all patients enrolled into the study.

Programming note: Add the mITT population if analyst decides it is needed later.

Westat (Created on DDMMYYYY)
S:\TMB311\DA\SAS\L PATDISP.SAS

Safety (SAF) Population consists of patients receiving at least one partial dose of study drug.

Listing 16.2.1.2 Study Discontinuation

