# 3c=Missing data during the window but on study

[3] Failure to achieve/maintain response=Patient does not have >=0.5 log10 decline from baseline(BL) by Week 12 on study drug OR patient has a 0.5 log10 decline from BL prior to Week 12 but fails to maintain the 0.5 log10 decline from BL with a <1 log10 increase from nadir on any two consecutive scheduled efficacy assessments after Week 12.

Rebound=Patient has a >=0.5 log10 decline from BL by Week 12 that is maintained but viral load remains >=50 copies (not suppressed), followed by >=1 log10 increase from nadir at two consecutive scheduled visits any time after the primary endpoint.

Breakthrough=Patient has suppressed viral load (< 50 copies) at any time after primary endpoint followed by >=200 copies at two consecutive scheduled efficacy assessments.

[4]Suboptimal Response=Patient has a 0.5 log10 decline but does not suppress (<50 copies) at any time after primary endpoint; Virologic Suppression=Patient has a 0.5 log10 decline and does suppress (<50 copies) at any time after primary endpoint

Programming note: See footnotes (values to the left of the =) to indicate what values will be displayed in the listing.

Westat (Created on DDMMMYYYY)
S:\TMB311\DA\SAS\L VLOUTCOMES.SAS

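### SAP 3.3.3 gives the two investigator-sponsored IND patients in Cohort 1 an on-ibalizumab Baseline, contradicting protocol 9.4, so one who enters and stays suppressed can be listed as a virologic failure

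*SAP*

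**What the plan says.** Protocol 9.4 has three Baseline rules. TMB-202 and TMB-301 rollovers keep the Baseline of the earlier study. Cohort 2 uses TMB-311 Day 0. For the remaining Cohort 1 patients, "Baseline values for TMB-311 are defined as the last values recorded prior to receiving the first dose of ibalizumab".

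SAP 3.3.3 repeats the first rule but puts the remaining Cohort 1 patients with Cohort 2: "Baseline is defined as the last assessment prior to their first dose of study drug on the TMB-311 Day 0 visit". The Cohort 1 entry criterion in protocol 5.1 is that patients "Are currently receiving ibalizumab via other TaiMed-sponsored or Investigator-sponsored IND protocol", so for them this is an on-treatment value.

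Several outcomes depend on Baseline:

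- **Virologic failure.** SAP 2.1 defines it as "two consecutive measurements beginning at Week 24 or later if less than a 0.5 log10 decline from the Baseline viral load". Protocol 3.1 uses the same threshold and adds "see Section 9.4 for the definition of Baseline".
- **Snapshot outcome.** Category 2a in SAP 4.5.2.3 is a change of less than 0.5 log10, measured as "copies/mL drop from Baseline in viral load". Category 1 (success) needs at least 0.5.
- **Failure to achieve or maintain response.** The outcome listing footnote gives its first arm as "Patient does not have >=0.5 log10 decline from baseline(BL) by Week 12 on study drug".
- **Missing Equals Failure (SAP 3.3.4).** A missing viral load, and every visit after confirmed failure, takes the Baseline value.
- **CD4+ toxicity (SAP 4.5.2.4).** It requires two consecutive counts under 200 that are also a 50% reduction from Baseline.

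SAP 4.5.2 extends the secondary endpoints to all cohorts. SAP 3.4.1 puts the two former investigator-sponsored IND patients in listings only, and the programming notes confirm that "the listings should also include the 2 PI-IND rollover patients".

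**The concern.** The two documents give different Baselines for the same patients, and the SAP does not mark this as a departure. It does announce another one, the extension of the secondary endpoints to Cohort 1, so the silence here suggests an oversight.

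The SAP rule also sits badly with the rest of the SAP. The other Cohort 1 patients keep a pre-treatment Baseline, and SAP 4.3.1 counts Cohort 1 exposure from the first dose in the previous study. Only this subgroup has its reference point moved to TMB-311 entry.

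A decline from Baseline measures response only if Baseline precedes treatment. Once the drug effect is inside Baseline, a patient who entered suppressed has almost no room to fall. Continued suppression then looks like non-response, and the row in the SAP listing can contradict the failure status that protocol 3.1 and 9.4 give for the same patient.

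**Working it through.** The documents state no figure to reproduce here. The check applies the SAP's own rules under each Baseline.

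**Inputs**

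- Threshold: a 0.5 log10 decline (SAP 2.1 and 4.5.2.3).
- Rounding: each log10 value is rounded to one decimal before the change is taken (SAP 4.4).
- Suppression: below 50 copies/mL (SAP 4.5.2.3). I use 49 as the example.
- Pre-ibalizumab viral load: not given for these two patients. I assume 1,000 copies/mL (the Cohort 2 entry floor, protocol 5.1) to 35,350 copies/mL (the TMB-301 median, protocol 1.2).

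**Formula:** drop = round(log10 Baseline, 1) − round(log10 follow-up, 1).

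**SAP Baseline, 49 copies/mL at Day 0.** log10(49) = 1.69, rounded to 1.7.

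- Follow-up 49: 1.7 − 1.7 = 0.0.
- Follow-up 40: 1.7 − 1.6 = 0.1.
- Follow-up 20: 1.7 − 1.3 = 0.4.
- Follow-up needed for a drop of 0.5: a rounded value of 1.2 or less, so below 10^1.25 = 17.8 copies/mL. (Without rounding it would be 49/10^0.5 = 15.5.)

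A patient who stays suppressed at about 18 copies/mL or more therefore never reaches 0.5. That patient falls in 2a, meets the first arm of failure to achieve response, and meets the two-consecutive-measurements rule from Week 24. The SAP's virologic suppression category is closed to the patient, because it also requires the 0.5 log10 decline.

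**Protocol Baseline, the same patient at 49 copies/mL.**

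- Baseline 1,000: 3.0 − 1.7 = 1.3.
- Baseline 35,350: log10 = 4.55 (4.548 before rounding), rounded to 4.5; 4.5 − 1.7 = 2.8.
- Smallest Baseline that gives success at 49: a rounded value of 2.2, so about 10^2.15 = 141 copies/mL (155 without rounding).

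**Missing Equals Failure.** Replacing a missing value with a Baseline of 49 gives a drop of 0.0, still a failure on the decline scale. On the copies/mL scale the imputed value is below 50. A patient who rebounded and left would thus carry suppressed imputed values.

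**CD4+ toxicity, illustration only.** Protocol 1.2 gives a TMB-301 median Baseline of 73 cells and a mean gain of 63. Assume a patient with 73 before treatment and 73 + 63 = 136 on drug. Half of 136 is 68 and half of 73 is 36.5. Two consecutive counts of 65, at least 14 days apart, would meet the flag against the on-drug Baseline but not against the pre-treatment one.

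**The case against.** The strongest reply is about reach. Only two patients are affected, and SAP 3.4.1 keeps them out of every displayed group, including the Total. They are neither pooled nor compared with anyone. That stands, and it rules out several stronger readings.

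- **That tables, figures or the primary endpoint are biased.** The Day 7 endpoint is Cohort 2 only, and the below-50 and below-400 proportions appear in tables and figures that omit these two patients. The Missing Equals Failure problem changes no reported proportion.
- **That misclassification is certain at every key visit.** Nothing says that either patient was suppressed at entry. The available text gives no rule for values below the quantitation limit. From 49, a substituted 10 or 15 gives a drop of 0.7 or 0.5 and passes; 20 or 25 gives 0.4 or 0.3 and fails. The visible part of the outcome listing is headed for the end-of-study visit, so repeated errors by visit cannot be confirmed.
- **That a Day 0 value necessarily exists.** Protocol Tables 3-1 and 3-3 schedule viral load and CD4+ at Screening/Day 0, but a SAP laboratory-listing footnote says Cohort 1 had no Screening samples, and SAP 3.3.4 bars imputing them. Baseline might then be an earlier on-drug value or missing, in which case no outcome can be derived.
- **That patients would be wrongly discontinued.** Protocol 3.1 sends sites to Section 9.4, so the SAP does not alter that decision.
- **That the CD4+ flag is reversed.** If counts rose on treatment, an on-drug Baseline makes the flag easier to meet. It does not invert it.

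None of this answers the contradiction between the two definitions.

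**Conclusion.** The contradiction is real, and the SAP's rule is unsuitable for patients already on the drug. Its size is small: the Baseline-dependent entries (virologic outcome, change from Baseline, CD4+ toxicity) in the listing rows of two patients.

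The failure label is conditional. It follows if the patient is suppressed at TMB-311 entry, a Day 0 or other on-drug value is used as Baseline, and later values as recorded or substituted do not fall below the threshold (about 18 copies/mL for entry at 49). The contrast with a success of 1.3 to 2.8 log10 rests on the assumed pre-ibalizumab range, but any pre-treatment value of about 141 copies/mL or more gives the same classification at 49 copies/mL. It is worth correcting because each patient's row is read individually and could contradict the status under the protocol.

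**What to change.** In SAP 3.3.3, restore the protocol 9.4 definition for Cohort 1 patients from neither TMB-202 nor TMB-301: the last values before the first ibalizumab dose, taken from the investigator-sponsored IND records. Keep the Day 0 rule for Cohort 2 only. Where no pre-ibalizumab value can be retrieved, list virologic outcome, change from Baseline and CD4+ toxicity as not evaluable, and do not substitute a TMB-311 Day 0 value.

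The cost is a short edit to one SAP section and a records request for two patients. The documents do not say whether the sponsor holds or can obtain those records, so the downside is that some of these rows may end up not evaluable.
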